5.3. Withdrawal Criteria

Subjects may withdraw from the study at any time prior to the subject’s expected completion and for any reason without prejudice to further treatment. Subjects considered treatment failures will be withdrawn from the study to receive appropriate alternative treatment.

A subject’s participation in the study may be discontinued at any time prior to the subject’s expected completion at the discretion of the Investigator or Sponsor. Reasons for removing a subject from the study include, but are not limited to, the following:

- The subject is uncooperative in adhering to the protocol requirements, including failure to participate in rehabilitation;
- The Investigator believes it is in the best interests of the subject;
- The subject withdraws consent.

The Investigator will attempt to document the subject’s reason for withdrawal on the study completion CRF.

If a subject fails to attend study visits, every attempt shall be made to contact the subject prior to considering the subject lost to follow up and withdrawing the subject from the study.

Subjects who are withdrawn from the study will not be replaced.

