6.2. Study Visits and Procedures

The schedule of events for subjects in this study is shown in Section 14. Subjects will be followed a total of 2 years following the index procedure. The study will close when the last subject entering the trial has completed the last study follow-up.

a. Screening Visit (Study Visit 1); within 4 weeks of the procedure

Subjects will be preliminarily screened for inclusion in the study when the Investigator evaluates them for knee pain. If a subject qualifies for inclusion in the study by meeting **all** of the screening inclusion criteria and meeting **none** of the exclusion criteria, then the study procedure, including the risks and benefits of participation, will be discussed with the subject. If the subject consents to participate, written informed consent with the Subject Informed Consent Form (see Appendix 5) will be obtained prior to initiating any tests or assessments not otherwise considered standard-of-care for the condition for which he or she is being evaluated.

The Subject will be provided with a copy of the signed Subject Informed Consent Form. The original will be kept in a secure location at the study site. If the Subject is subsequently enrolled in the study, a copy of the Subject's signed Subject Informed Consent Form will be placed in the Subject's study binder along with completed CRFs. Study binders will be stored in a secure location. In order to maintain Subject confidentiality, the Sponsor will not receive a copy of the signed Subject Informed Consent Form and will rely on the Investigator to ensure that ALL Subjects have reviewed and signed the Subject Informed Consent Form prior to collecting any study-directed information or undergoing any study-directed treatment.

If a subject qualifies for inclusion in the study by meeting **all** of the screening and preoperative baseline clinical inclusion criteria and meeting **none** of the pre-arthroscopy exclusion criteria, the subject will be provisionally enrolled and scheduled for arthroscopy. The subject's demographic information relevant to study variables will be collected at the Screening Visit. Subjects will also complete KOOS, IKCD Subjective Knee Evaluation, Lysholm Knee Questionnaire and Tegner Activity Scale outcome assessments.

b. Surgery and Rehabilitation (Study Visit 2)

Arthroscopy Procedure

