Investigator-specific standard-of-care arthroscopy will be performed. Intraoperative eligibility criteria will be evaluated. If **all** of the arthroscopy inclusion criteria are met and **none** of the arthroscopy exclusion criteria are met, the subject will be eligible for study enrollment. The subject is officially enrolled in the trial when the meniscal repair is completed.

Meniscal Repair Procedure

The Investigator will follow standard all-inside and/or inside-out, and/or outside-in, and/or NovoStitch arthroscopic procedures:

- Recommended spacing of sutures is 5mm;
- Video, still photographs and diagrams of the arthroscopy procedure will be captured for documentation of meniscal tear, tear preparation and tear treatment parameters. Images and diagrams will be provided to the sponsor. All patient identifying information should be removed prior to transferring images to the sponsor.

The ISAKOS Questionnaire documenting details of the meniscus tear and required excision (if any) will be completed (CRF-004, Details of Pathology). Details of the procedure will be documented (CRF-005, Details of Procedure) will be completed. It contains questions regarding the following:

- Number and configuration of sutures used;
- Repair technique and instruments;
- Meniscal repair time recorded from intraarticular introduction of suture to transection of final suture knot;
- Other intraoperative findings.

Rehabilitation Procedure

All subjects will follow their Investigator's preferred rehabilitation plan based on the particular tear and repair characteristics. At a minimum, all subjects must meet the following post-operative thresholds:

- Weight bearing as tolerated
- Hinged knee brace locked in extension when walking (4-6 weeks), released to 90 degrees for sitting/driving
- No squatting or stand up/sit down motions until after 6 weeks post-op
- No cutting or pivot sports until after 6 months post-op

c. First Follow-up [7-15 days] (Study Visit 3)

Subjects will be evaluated and a safety follow-up will be completed.

d. Second Follow-up [90 Day \pm 7 days] (Study Visit 4)

All subjects will be evaluated and a safety follow-up form will be completed. In addition all subjects will complete the following:

- KOOS
- IKCD Knee Evaluation
- Lysholm Knee Questionnaire
- Tegner Activity Scale

e. Third Follow-up [185 Day \pm 14 days] (Study Visit 4)

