9. STATISTICAL PLAN

9.1. Subject Population(s) for Analysis

Data obtained from all enrolled subjects will be analyzed on a per-treatment (PT) basis, which will include all enrolled subjects who receive the protocol-defined treatment of suture-based meniscal repair.

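### Protocol 5.3 lets the Investigator or Sponsor end follow-up for non-adherence although the repair is already complete, and the SAP carries that loss into the later-visit results

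*Protocol*

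**What the plan says.** Protocol 5.3 allows participation to be ended at any point before "expected completion at the discretion of the Investigator or Sponsor". It introduces the grounds with "Reasons for removing a subject from the study include, but are not limited to, the following", and the first of them is "The subject is uncooperative in adhering to the protocol requirements, including failure to participate in rehabilitation". The other two are the Investigator's view of the subject's best interests and withdrawn consent. For missed visits it requires all efforts at contact "prior to considering the subject lost to follow up and withdrawing the subject from the study". Withdrawn subjects are not replaced, and the Investigator is to try to record the reason on the study completion form.

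Protocol 6.2 fixes the moment of enrolment: "The subject is officially enrolled in the trial when the meniscal repair is completed". Protocol 9.1 names the analysis population as "all enrolled subjects who receive the protocol-defined treatment of suture-based meniscal repair"; rehabilitation is not part of that definition. Protocol 6.2 sets minimum post-operative thresholds for everyone, on top of each Investigator's "preferred rehabilitation plan based on the particular tear and repair characteristics". On duration it says: "Subjects will be followed a total of 2 years following the index procedure".

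No section provides for collecting reoperation status or patient-reported outcomes after removal. Protocol 8.2 mentions vital status only, and only for subjects who revoke authorization.

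In the SAP, 7.3 analyses data as observed cases. Section 7.4 divides by the subjects whose repair status is known at the visit. Section 7.2 leaves out of the Analysis Population anyone with a significant deviation or an early withdrawal. Section 7.9 has no sensitivity analysis for removed subjects.

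**The concern.** In a drug trial, discontinuing a subject may at least stop an exposure. Here the treatment is one operation, finished before the subject counts as enrolled, so removal affects only what is observed afterwards.

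The decision is also not independent of outcome. The study is open label, and the Investigator who may remove a subject also examines the knee. Subjects who skip rehabilitation are plausibly at higher risk of a failed repair, and pain from a failing repair is itself a reason to stop rehabilitation. Both links are inferences; the documents give no failure rate by adherence. If they hold, the subjects lost are disproportionately those who would have been reoperated, and the later-visit figures look better than the experience of everyone who received the repair, which is the population Protocol 9.1 names. With 30 planned subjects, each one is worth more than 3 percentage points (1/30 = 3.3%).

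**Working it through.** **1. No figure in the plan to reproduce.** SAP 6.1 states that 30 subjects were planned without a formal calculation, and neither document gives an expected reoperation or dropout rate. What follows is illustration under stated assumptions.

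**2. How a removal reaches the endpoint.** A subject removed before any reoperation has unknown status at later visits. Under SAP 7.4 that subject leaves both numerator and denominator from then on, but still counts at visits before removal. Under SAP 7.2 the same subject leaves the Analysis Population as an early withdrawal.

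**3. Size of the shift.** Let N be the treated subjects and k those removed before any event, and let p_r and p_s be the reoperation proportions among removed and remaining subjects. Then

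observed rate - full-cohort rate = (k/N) × (p_r - p_s).

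Assume N = 30, 6 reoperations by 2 years and k = 3. The full-cohort rate is 24/30 = 80.0% (Clopper-Pearson 95% CI 61.4 to 92.3).

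| Removed who would have been reoperated | Observed | 95% CI | Shift = (3/30) × (p_r - p_s) |
|---|---|---|---|
| 0 of 3 | 21/27 = 77.8% | 57.7 to 91.4 | 0.1 × (0 - 6/27) = -2.2 points |
| 1 of 3 | 22/27 = 81.5% | 61.9 to 93.7 | 0.1 × (1/3 - 5/27) = +1.5 points |
| 2 of 3 | 23/27 = 85.2% | 66.3 to 95.8 | 0.1 × (2/3 - 4/27) = +5.2 points |
| 3 of 3 | 24/27 = 88.9% | 70.8 to 97.6 | 0.1 × (1 - 3/27) = +8.9 points |

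The 1-of-3 row is a risk ratio of (1/3)/(5/27) = 1.8. The 3-of-3 row needs (3/3)/(3/27) = 9.

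**4. The same formula on other assumptions.** Take N = 27, the number left after the 3 exclusions in SAP 6.1, and assume a reoperation rate of 10% to 20% in those who stay and two to three times that in those removed. The smallest case is k = 3, 10%, doubled: (3/27) × 0.10 = 1.1 points. The largest is k = 5, 20%, tripled: (5/27) × 0.40 = 7.4 points. If the risks are equal the expected bias is zero.

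**5. What bounding rows would show.** Assume 27 subjects, 3 removed with unknown status, and 3 reoperations among the other 24:

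- observed cases: 21/24 = 87.5% (67.6 to 97.3)
- removed counted as all free: 24/27 = 88.9% (70.8 to 97.6)
- removed counted as all reoperated: 21/27 = 77.8% (57.7 to 91.4)

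The bounds lie 11.1 points apart, a spread that the observed-case line does not show.

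**The case against.** The strongest reply is that this is a common permissive clause with no documented use. That stands: 5.3 says participation may be ended, and neither document reports anyone removed under it. A reader might take the 3 subjects excluded in SAP 6.1 as such removals. The text attributes them to protocol deviations and does not connect them with 5.3; that the illustration above also goes from 30 to 27 is coincidence.

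Parts of the plan already help. Protocol 5.3 asks for contact efforts before a subject is declared lost, and for the withdrawal reason to be recorded. SAP 7.6 lists withdrawal reasons and 7.7 summarises deviations. These make removals visible, but they supply no outcomes after removal, and the contact duty does not reach discretionary removal.

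Other stronger readings are not supported either:

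- That the results would describe adherent subjects only. Removed subjects still count at visits where their status is known, and Protocol 9.1 keeps every treated subject in its population.
- That removal rests on mere impression because no listed case report form is titled for rehabilitation. The contents of the forms are not in the supplied text, and Protocol 6.2 gives concrete thresholds.
- That 5.3 contradicts the two-year follow-up. Two years is the planned duration, and a withdrawal clause is compatible with it.

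The shift is also small beside the sampling error: the intervals in the table are about 27 to 34 points wide, in a study with no formal hypothesis. That tempers the importance, but an interval computed on the remaining subjects does not account for selective loss.

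**Conclusion.** The point holds as a possible, avoidable bias, not as a demonstrated one. The protocol permits follow-up to end for non-adherence after treatment is complete, nothing provides for outcomes thereafter, and SAP 7.2, 7.3 and 7.4 pass the loss on to freedom from reoperation and score changes at later visits.

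The direction is upward only if removed subjects fail more often than those who stay. With 3 of 30 removed and 6 reoperations in all, the shift is about +1.5 points when 1 of the 3 would have been reoperated, with extremes of -2.2 and +8.9. The upper extreme should not be read as the expected effect, because it requires every removed subject to fail. The counts of removals and reoperations are assumptions, since the documents give neither. The separate statement in 5.3 about withdrawing treatment failures is a different route to lost data and is not counted here.

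**What to change.** In Protocol 5.3, delete non-adherence, including non-participation in rehabilitation, as a reason to end follow-up. Record it as a deviation and continue collecting reoperation status and patient-reported outcomes to Day 730, unless consent is withdrawn or the Investigator judges removal to be in the subject's best interests. The rehabilitation requirements themselves stay as they are.

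The SAP must change as well. Otherwise a non-adherent subject kept in follow-up and logged on the deviation form (CRF-010) could still be dropped through 7.2, which does not define a significant deviation.

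- In 7.2, state that rehabilitation non-adherence, or removal by the Investigator or Sponsor, does not exclude a treated subject from the primary endpoint analysis.
- Add last known reoperation status to the 7.6 listing for each removed subject.
- In 7.9, add two rows for freedom from reoperation, with removed subjects of unknown status counted as all free and as all reoperated. These are bounds, not estimates.

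The cost is a sentence or two in the protocol, one in the SAP, a listing column and two table rows. The reported rate may come out slightly less favourable. On timing, SAP 6.1 (version dated 4 September 2019) says the sample had been accrued, so a protocol edit cannot by itself recover outcomes for anyone already removed. The SAP changes can still be applied to them.

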6. METHODS AND PROCEDURES

6.1. Method for Assigning Subjects

This trial is a single-arm, nonrandomized, open label study; assignment and blinding procedures are not required.

6.2. Study Visits and Procedures

The schedule of events for subjects in this study is shown in Section 14. Subjects will be followed a total of 2 years following the index procedure. The study will close when the last subject entering the trial has completed the last study follow-up.

a. Screening Visit (Study Visit 1); within 4 weeks of the procedure

Subjects will be preliminarily screened for inclusion in the study when the Investigator evaluates them for knee pain. If a subject qualifies for inclusion in the study by meeting **all** of the screening inclusion criteria and meeting **none** of the exclusion criteria, then the study procedure, including the risks and benefits of participation, will be discussed with the subject. If the subject consents to participate, written informed consent with the Subject Informed Consent Form (see Appendix 5) will be obtained prior to initiating any tests or assessments not otherwise considered standard-of-care for the condition for which he or she is being evaluated.

The Subject will be provided with a copy of the signed Subject Informed Consent Form. The original will be kept in a secure location at the study site. If the Subject is subsequently enrolled in the study, a copy of the Subject's signed Subject Informed Consent Form will be placed in the Subject's study binder along with completed CRFs. Study binders will be stored in a secure location. In order to maintain Subject confidentiality, the Sponsor will not receive a copy of the signed Subject Informed Consent Form and will rely on the Investigator to ensure that ALL Subjects have reviewed and signed the Subject Informed Consent Form prior to collecting any study-directed information or undergoing any study-directed treatment.

If a subject qualifies for inclusion in the study by meeting **all** of the screening and preoperative baseline clinical inclusion criteria and meeting **none** of the pre-arthroscopy exclusion criteria, the subject will be provisionally enrolled and scheduled for arthroscopy. The subject's demographic information relevant to study variables will be collected at the Screening Visit. Subjects will also complete KOOS, IKCD Subjective Knee Evaluation, Lysholm Knee Questionnaire and Tegner Activity Scale outcome assessments.

b. Surgery and Rehabilitation (Study Visit 2)

Arthroscopy Procedure

Investigator-specific standard-of-care arthroscopy will be performed. Intraoperative eligibility criteria will be evaluated. If **all** of the arthroscopy inclusion criteria are met and **none** of the arthroscopy exclusion criteria are met, the subject will be eligible for study enrollment. The subject is officially enrolled in the trial when the meniscal repair is completed.

Meniscal Repair Procedure

The Investigator will follow standard all-inside and/or inside-out, and/or outside-in, and/or NovoStitch arthroscopic procedures:

- Recommended spacing of sutures is 5mm;
- Video, still photographs and diagrams of the arthroscopy procedure will be captured for documentation of meniscal tear, tear preparation and tear treatment parameters. Images and diagrams will be provided to the sponsor. All patient identifying information should be removed prior to transferring images to the sponsor.

The ISAKOS Questionnaire documenting details of the meniscus tear and required excision (if any) will be completed (CRF-004, Details of Pathology). Details of the procedure will be documented (CRF-005, Details of Procedure) will be completed. It contains questions regarding the following:

- Number and configuration of sutures used;
- Repair technique and instruments;
- Meniscal repair time recorded from intraarticular introduction of suture to transection of final suture knot;
- Other intraoperative findings.

Rehabilitation Procedure

All subjects will follow their Investigator's preferred rehabilitation plan based on the particular tear and repair characteristics. At a minimum, all subjects must meet the following post-operative thresholds:

- Weight bearing as tolerated
- Hinged knee brace locked in extension when walking (4-6 weeks), released to 90 degrees for sitting/driving
- No squatting or stand up/sit down motions until after 6 weeks post-op
- No cutting or pivot sports until after 6 months post-op

c. First Follow-up [7-15 days] (Study Visit 3)

Subjects will be evaluated and a safety follow-up will be completed.

d. Second Follow-up [90 Day \pm 7 days] (Study Visit 4)

All subjects will be evaluated and a safety follow-up form will be completed. In addition all subjects will complete the following:

- KOOS
- IKCD Knee Evaluation
- Lysholm Knee Questionnaire
- Tegner Activity Scale

e. Third Follow-up [185 Day \pm 14 days] (Study Visit 4)

All subjects will be evaluated, and a safety follow-up form will be completed. In addition all subjects will complete the following:

- KOOS

- IKCD Knee Evaluation
- Lysholm Knee Questionnaire
- Tegner Activity Scale

Where available, subjects will undergo an in-office arthroscopy (i.g. VisonScope) to assess the tissue repair. Clinical follow-up should continue with or without the arthroscopy.

f. Fourth Follow-up [365 Day \pm 30 days] (Study Visit 5)

All subjects will be evaluated, a safety follow-up form will be completed and an MRI will be performed. In addition all subjects will complete the following:

- KOOS
- IKCD Knee Evaluation
- Lysholm Knee Questionnaire
- Tegner Activity Scale

g. Fifth Follow-up [730 Day \pm 30 days] (Study Visit 6)

All subjects will be evaluated, a safety follow-up form will be completed and a Standing AP x-ray will be obtained for evaluation of joint space narrowing. In addition all subjects will complete the following:

- KOOS
- IKCD Knee Evaluation
- Lysholm Knee Questionnaire
- Tegner Activity Scale

7. SAFETY MEASUREMENTS

7.1. Definitions

Complication

A complication is any untoward medical occurrence, unfavorable and unintended sign (including clinically significant abnormal laboratory finding), symptom, or condition experienced by the subject and temporally associated with the procedure whether or not considered related to the procedure.

Major Complication

Any complication attributable to the meniscal repair procedure that, in the view of either the Investigator or Sponsor, results in any of the following outcomes:

- Death;
- Life-threatening illness or injury;
- Inpatient hospitalization or prolongation of existing hospitalization;
- Persistent or significant incapacity or substantial disruption of the ability to conduct normal life functions;

- Important medical events that, based upon appropriate medical judgment, require medical or surgical intervention to prevent one of the above outcomes.

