7.2. Collecting, Recording and Reporting of Complications

At each contact with the subject, the Investigator will seek information on complications by specific questioning and, as appropriate, by examination. All complications definitely, probably or possibly involving the treated knee, as well as any required remedial action shall be recorded on the subject's appropriate CRF. The investigator will also be asked to assess the complication with respect to severity and relatedness to the procedure.

The minimum initial information to be captured in the subject's source document concerning the complication includes:

- Study identifier;
- Study center;
- Subject number;
- A description of the complication;
- Date of onset;
- Investigator assessment of the association between the complication and study treatment (relatedness);
- Investigator assessment of severity;
- Current status;
- Whether the complication is a major complication and reason for this classification.

The clinical course of each complication should be recorded and followed until resolution, stabilization, or until it has been determined that the surgical repair is not the cause.

Notification of Sponsor by Investigator

The Investigator shall notify the Sponsor of any Major Complication experienced by any subject entered into the study. Such Major Complications ***must*** be reported ***within 24 hours*** to the following:

Ceterix Orthopaedics [name] [name] [contact] [contact]

Within the following 48 hours, the Investigator shall provide further information, as applicable, in the form of a written narrative. As the Investigator learns it, significant new information shall be provided on an ongoing basis to the Sponsor.

Notification of IRB by Investigator

With one exception noted at the end of Section 7.2, all communication with an IRB is the responsibility of the Investigator. Investigator will comply with all IRB requirements for the reporting of complications. Copies of each report and documentation of IRB notification and receipt will be kept in the Investigator's study file.

An Investigator shall report to the Sponsor a withdrawal of approval by the Investigator's reviewing IRB as soon as a possible, but no later than 5 working days of the IRB notification of withdrawal.

Notification of Investigators and IRBs by Sponsor

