5.2 Safety Endpoint(s)

Safety follow-up includes reporting of a:

Complication

A complication is any untoward medical occurrence, unfavorable and unintended sign (including clinically significant abnormal laboratory finding), symptom, or condition experienced by the subject and temporally associated with the procedure whether or not considered related to the procedure.

Major Complication

Any complication attributable to the meniscal repair procedure that, in the view of either the Investigator or Sponsor, results in any of the following outcomes:

- Death;
- Life-threatening illness or injury;
- Inpatient hospitalization or prolongation of existing hospitalization;

CONFIDENTIAL AND PROPRIETARY

This document contains information that is confidential and proprietary to Smith & Nephew PLC and Smith & Nephew, Inc. and is intended for use only by Smith & Nephew and its manufacturer. It shall not be reproduced or copied in whole or in part, nor shall the contents be disclosed by any means without prior written permission from Smith & Nephew, nor shall anyone make any use of it that is contrary to the expressed or implied wishes of Smith & Nephew

Statistical Analysis Plan	Smith+Nephew
A Prospective, Non-randomized, Multi-Center Investigation of All-suture-based Repair of Horizontal Meniscal Tears (STITCH Study)	Number: CTX-CP001
	Version: 1, 4-Sept-2019
	Page: 7 of 15

- Persistent or significant incapacity or substantial disruption of the ability to conduct normal life functions;
- Important medical events that, based upon appropriate medical judgment, require medical or surgical intervention to prevent one of the above outcomes.

6. Statistical Considerations

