- the incidence according to subjects with at least one new complication,
- the incidence according to subjects with at least one new major complication,
- the incidence according to subjects whose complication was related to fall or injury,
- the incidence according to subjects who had at least one complication possibly, probably, or definitely related to surgical procedure,
- the incidence according to subjects who had at least one complication possibly, probably, or definitely related to meniscal repair, and
- the incidence according to subjects who had at least one complication possibly, probably, or definitely related to device(s) used.

A summary table will be presented that summarizes the complications by code according to subjects who had at least one new complication of a particular code.

In addition, for each complication, the following will be summarized: the relationship to the surgical procedure, the relationship to meniscal repair, the relationship to device(s) used, outcome and duration of the resolved complications and the duration of the complications at study discontinuation.

A listing of all new complications per subject will also be presented, along with duration, major complication status (yes/no), resolution status (resolved or ongoing), and relatedness to surgical procedure, meniscal repair, and device(s) used.

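### Major status requires attribution to the repair, so serious events judged unrelated carry no 24-hour Sponsor notice, and the SAP's two rules for 'major' give no all-cause serious count

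*Protocol*

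**What the plan says.** Protocol 7.1 defines an ordinary complication without regard to cause: it need only be "temporally associated with the procedure whether or not considered related to the procedure". The Major category is narrower. It covers only an event "attributable to the meniscal repair procedure that, in the view of either the Investigator or Sponsor, results in any of the following outcomes". Five outcomes follow: death, threat to life, hospitalisation, lasting incapacity, and events needing intervention to prevent one of these. SAP 5.2 carries the same condition ("Any complication attributable to the meniscal repair procedure that, in the view of either the Investigator or Sponsor").

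Protocol 7.2 builds the urgent route on this term. "The Investigator shall notify the Sponsor of any Major Complication experienced by any subject entered into the study", and the time limit is explicit: "Such Major Complications *must* be reported *within 24 hours* to the following". For the CRF the scope is different: "All complications definitely, probably or possibly involving the treated knee, as well as any required remedial action shall be recorded on the subject's appropriate CRF". Separate items in the 7.2 source-document list cover relatedness, severity and Major status, with relatedness and severity assessed by the Investigator.

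On analysis, SAP 7.10 (Analysis of Safety Endpoints) will tabulate "the incidence according to subjects with at least one new major complication". SAP 7.4 (Derived Data) gives a rule for the flag. It is set by a yes to any one of: related to a fall or injury, related to the surgery, related to the repair, related to a device, resolved, not resolved, or death.

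**The concern.** Seriousness is a fact about what happened to the subject; relatedness is a judgement about why. Expedited reporting usually follows the first, so that someone other than the treating surgeon can examine the second. Here the judgement comes first. In an open-label, single-arm study the Investigator who did the repair assesses relatedness, and Protocol 7.3 b leaves safety oversight to each Investigator at his or her own site. The documents describe no independent safety review. An event with a listed outcome that is judged unrelated drops out of the urgent route.

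Two things are at stake: whether the Sponsor hears of such events in time to form its own view, and whether the final report can say how many treated subjects had a serious event from any cause.

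**Working it through.** The plan states no figure on this point, so there is nothing to reproduce. The check runs hypothetical serious events through the rules as written.

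**Cases.** Three outcomes (death; hospitalised and resolved; hospitalised and ongoing), attributed to the repair or not, involving the treated knee or not: 3 × 2 × 2 = 12 combinations. The three outcomes behave alike, so four rows suffice.

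| Attributed to repair | Involves treated knee | Major with 24-hour notice (Protocol 7.1, 7.2) | Complication CRF required (Protocol 7.2) | In major row, SAP 5.2 rule | In major row, SAP 7.4 rule |
|---|---|---|---|---|---|
| Yes | Yes | Yes | Yes | Yes | Yes |
| Yes | No | Yes | No | Only if recorded | Only if recorded |
| No | Yes | No | Yes | No | Yes |
| No | No | No | No | No | Only if recorded |

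**Results for the 6 combinations not attributed to the repair.**

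1. Urgent notice: 0 of 6 are Major, so 0 of 6 carry the 24-hour duty.
2. CRF: 3 of 6 must be recorded (those involving the knee). The other 3 need not be, and so may be missing from every complication row. The cause there is the treated-knee limit in 7.2, not the Major definition.
3. SAP row programmed from 5.2: 0 of 6 appear.
4. SAP row programmed from 7.4: the 3 recorded events all appear, because resolved, not resolved and death each set the flag. For the same reason nearly every other recorded complication sets it too, so the major row nearly equals the any-complication row. Hospitalisation, threat to life and incapacity are not terms of the flag.

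Neither rule yields a count of subjects with a listed serious outcome regardless of cause, and SAP 7.10 has no other row that does.

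**Scale.** The 95% Clopper-Pearson limits for x events in n subjects are the 0.025 quantile of Beta(x, n − x + 1) and the 0.975 quantile of Beta(x + 1, n − x). With x = 0 the lower limit is 0 and the upper limit is 1 − 0.025^(1/n). The planned number is 30 (Protocol 5.1). SAP 6.1 excludes 3 subjects from all analyses, while SAP 7.2 bases safety on all treated subjects, so n = 30 − 3 = 27 is shown as well.

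| Row | n = 30 | n = 27 |
|---|---|---|
| 0 events | 0.0% (0 to 11.6) | 0.0% (0 to 12.8) |
| 1 event | 3.3% (0.1 to 17.2) | 3.7% (0.1 to 19.0) |

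These limits show how far one event moves a row of this size. They do not predict that any event will occur.

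**The case against.** The best defence is that the documents leave other routes open, and several parts of it stand.

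- **The SAP row.** A reader might infer that an unrelated death or hospitalisation is simply absent from the major row. That follows only if the row is programmed from SAP 5.2. Under SAP 7.4 a fall and a death are both named triggers, and a recorded admission sets the flag as resolved or ongoing.
- **Direction of bias.** For the same reason the documents do not support a claim that the row can err only towards too few major complications. Under 7.4 the error is over-inclusion.
- **The Sponsor's view.** It would be too strong to say that it cannot operate in time. Protocol 8.1 has CRFs sent to the Sponsor promptly, though with no number of days, so later reclassification of a recorded event is possible. The phrase about the Investigator's or Sponsor's view also attaches to whether a listed outcome resulted; who decides attribution is left unclear.
- **Visibility.** SAP 7.10 has a row for fall- or injury-related complications, summarises outcomes and lists every new complication. SAP 7.6 lists withdrawal reasons. A death could well be seen in one of these.
- **Other channels.** IRB reporting under 7.2 concerns complications generally. The source-document list is not limited to the knee.
- **The 7.4 sentence.** Its parenthesis is not closed in the text available, so it may be a run-together list of separate flags. On that reading 7.4 gives no rule for Major and the row falls back on 5.2.

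None of this supplies a timed Sponsor notice for a serious event judged unrelated, a CRF duty for one outside the knee, or an all-cause serious count. It also matters that major complications are not a primary endpoint, and that index-site reoperation is analysed with no attribution test.

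**Conclusion.** The concern holds as a gap in expedited reporting, recording and tabulation. By Protocol 7.1 and 7.2, no serious event judged unrelated carries the 24-hour notice, and one that also lies outside the treated knee need not reach the complication CRF. A Sponsor view is therefore not assured in time. SAP 5.2 and 7.4 define the same row by incompatible rules: one omits unrelated serious events, and the other mixes them with nearly every recorded complication.

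The size cannot be stated as a bias, because its direction depends on which rule is programmed and on how many such events occur. One event is worth 3.3 points at n = 30, or 3.7 at n = 27. The conclusion rests on reading the 7.4 flag as printed and the treated-knee sentence in 7.2 as the limit on CRF recording. The protocol gap does not depend on the 7.4 reading. The change is inexpensive and should be made.

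**What to change.** 1. **Protocol 7.1 and SAP 5.2.** Delete the condition that the event be attributable to the repair, so that the listed outcomes alone set Major status. Record relatedness separately, as the list in Protocol 7.2 already allows.
2. **Protocol 7.2.** Apply the existing 24-hour report and CRF recording to every event with a listed outcome, whether or not the treated knee is involved. Without the second part, a serious event outside the knee could still be missing from the complication tables.
3. **SAP 7.4.** Replace the major flag with the SAP 5.2 outcome list. Changing 5.2 alone would leave the row nearly equal to all complications.
4. **SAP 7.10.** Show two rows: all major complications, and those judged at least possibly related, naming which relatedness item (procedure, repair or device) is meant. State the safety denominator, 30 or 27.

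The cost is wording, one extra row, a few more expedited reports and perhaps a less favourable all-cause rate; the related rate is still shown. SAP 6.1 says the sample was accrued, so the protocol changes may come too late for some subjects. The SAP changes can still be made for the 2-year report, with a Sponsor review of recorded complications and withdrawal reasons for listed outcomes. Events never recorded may not be recoverable, and the report should say so.
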